Sociodemographic Questionnaire. If a follow-up visit (telehealth or in-person) is conducted during the follow-up period, the clinical site will administer the AIRQ® three-month recall version (regardless of timing of follow-up visit). Sites/HCPs will complete a Clinical Case Report Form (CRF) after the initial visit and after the first follow-up visit (if conducted) for each participant. For the initial and first follow-up visit for which patients complete an AIRQ®, HCPs will be required to review the Assess component of the Asthma Checklist and provide their responses on the CRF; while sites are encouraged to use the AIRQ® for any additional follow-up visits during the study and to provide documentation of the AIRQ® scores, additional CRFs will not be completed by the HCPs.

Additionally, Evidera will host a 30-minute conference call with each clinical site for up to four timepoints (touchpoints) to discuss the implementation of PRECISION tools (i.e., frequency of visits to and the number of portable document format (PDF) file views from study website), assess whether sites are meeting their targets for using the telehealth platform, address site questions, and discuss any challenges of implementing the PRECISION program. These meetings will take place at Months 1, 2, 3 (optional), and 6 and will be used to identify any sites that may benefit from participating in a re-training session. The optional Month 3 touchpoint will be based on whether the site has any difficulties with the study.

Study Population: Clinic staff will invite patients age ≥ 13 years with an HCP-confirmed asthma diagnosis who present for a clinic visit (telehealth or in-person) to complete the AIRQ® and participant questionnaires. Each site will aim to recruit approximately 50 to 75 patients with a total sample size ranging from approximately 750 to 1,500 patients. The number of patients recruited from each site may be modified (i.e., able to recruit > 75 patients) to ensure that the target study sample size is obtained.

Inclusion Criteria: Patients must meet all of the following criteria to be eligible for enrollment:

1. ≥ 13 years of age at the time of enrollment
2. Prior diagnosis of HCP-confirmed asthma
3. Able to read, understand, and speak English or Spanish sufficiently to self-complete or be administered the AIRQ™ via telephone, desktop computer, or mobile device (e.g., smartphone, iPad)

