4.1.3.1 AIRQ®

The AIRQ® includes 10 questions concerning patient medication use, asthma symptoms, medical visits, and tests. All response options are in yes/no format with a two-week recall for symptom-based impairment questions (items 1–7) and 12-month recall for exacerbation-based risk questions (items 8–10). The AIRQ® was developed iteratively, and a targeted review of research articles, current asthma guidelines and screeners, grey literature, and a secondary analysis of qualitative patient data informed the initial development of the AIRQ®. Five clinical experts, representing primary care and specialty care (including an allergist/immunologist, two pulmonologists, a nurse PhD researcher, and a family practitioner), academic and community practices, and five geographic regions of the United States (US), participated in five web-based focus groups to further develop the AIRQ®. The AIRQ® was subsequently presented at six advisory board meetings, in which more than 141 clinical experts, practitioners, asthma educators, and patient advocates reviewed and provided additional suggestions for refinement. All participants will complete the AIRQ® at their initial visit, whether in-person or via telehealth. Scoring information is located in Appendix A.

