4.1.3.2 Follow-up AIRQ® (AIRQ® 3-month recall version)

A three-month recall version for the exacerbation items of the AIRQ® reduces the risk questions' (items 8–10) recall period to three rather than 12 months. Patients will complete the follow-up AIRQ® at all follow-up visits during the nine-month implementation period (if applicable).

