AIRQ® score and control level at the initial visit and Follow-up AIRQ® score and control level at follow-up visit(s) will be explored overall and by practice cluster, and presented using descriptive statistics (n, frequency, mean, SD) (Table 4a, Table 10a and Table 10j). The change in AIRQ® between initial visit and first follow-up visit will be evaluated using paired t-tests for the overall sample, and by practice cluster (Table 15). If the sample size allows, change in AIRQ® score will also be evaluated based on elapsed time from initial visit to follow-up by groups (e.g., 0–3 months; 4–6 months; 7–9 months). In Table 16, shift analyses will be conducted to evaluate change in AIRQ® control score between the initial and first follow-up visit. The frequency of patients improving, maintaining or worsening in AIRQ® control level from initial to first follow-up visit will be described in Table 17. Similarly, shift analyses for AIRQ® control score between the initial and final follow-up visit will be presented in Table 18, and the frequency of patients improving, maintaining or worsening in AIRQ® control level from initial to final follow-up visit will be described in Table 19. If the sample size for additional AIRQ® completions after the first follow-up allows, an additional exploratory analysis will be to explore the trajectory of change in AIRQ® score in relation to visit number and other clinical variables.

Statistical analysis plan
D2287L00028 (EVA-26645)

AstraZeneca
27 Sep 2023

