6. BIAS

6.1 Methods to Minimize Bias

Given that completing the ACE Questionnaire is optional, the potential for response bias (e.g., patients who like the telehealth platform may be more inclined to complete the survey) may be introduced into this study. This will be noted when interpreting the results. Additionally, patients who have a follow-up assessment may be more severe than those who do not; thus, change scores may not be representative of the entire sample, which will also be noted when interpreting results.

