Appendix A. Scoring Information

AIRQ®

The AIRQ® includes 10 questions with Yes/No responses. A total AIRQ® score is generated by summing the number of “Yes” responses. The scores for the AIRQ® range from 0–10. Patients with scores of 0 or 1 are considered “well-controlled,” patients with scores of 2–4 are considered “not well-controlled,” and patients with scores of 5–10 are considered “very poorly controlled.”

ACE

There are eight questions on the ACE with Likert scale responses (Strongly Agree, Agree, Disagree, Strongly Disagree), and one open-ended question. There is no total score for the ACE. Scores for each individual item will be described by frequency.

NAEPP Step Coding

Code	Maintenance Therapy	Rescue therapy
Step 1	No daily medication checked	SABA alone with no maintenance therapy ^a
Step 2	Low-dose ICS	SABA with maintenance therapy ^b
	Theophylline Preparations	
	Leukotriene modifier	
	No daily medication checked	ICS+ SABA as rescue therapy alone Fixed dose combination fast-acting LABA/ICS alone as rescue
Step 3	Medium/High-dose ICS	For Steps 3 through 6, step assignment is based on maintenance therapy only.
	Low-dose ICS + LAMA	
	Low-dose ICS+ leukotriene modifier	
	Low-dose ICS + theophylline preparation	
	Low dose ICS + LABA	
Step 4	Medium-dose ICS/LABA	
	Medium dose ICS + LAMA	
	Medium/high dose ICS + theophylline	
	Medium/high dose ICS + leukotriene modifier	
Step 5	High-dose ICS/LABA + LAMA	
	High-dose ICS/LABA	
Step 6 ^c	Any maintenance therapy AND	Chronic oral systemic corticosteroids OR Biologic

^a Possible alternative: “SABA as rescue therapy via nebulizer without other rescue or maintenance therapies” or “Primatene Mist as rescue and no maintenance therapy”

^b Possible Alternative: “SABA as rescue therapy via nebulizer with other rescue maintenance therapies” or “Primatene Mist as rescue with maintenance therapy(s)”

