Appendix B. Revisions to Select Analyses Initially Detailed in this SAP

Due to the nature of the data collected or to enhance clarity of presentation or interpretation of findings, some revisions were made to select analyses initially specified in the SAP. These revisions are detailed below:

- Novel site results were displayed in separate tables (N table series)
- All analyses by language were not conducted since the AIRQ was only administered in English language.
- There was no data on PRECISION education resource views/downloads for the specialty care cluster so tables 22c and 23c could not be run
- Some analyses could not be conducted due to the small sample size, e.g., for Tables 23e-23j, Tables 29b1-b3, Tables 29e-t, Table 30a, Table N4d, Tables N6b-N6i, Tables N7b-N7i, Table N8e, N10d, N22f, N23e, N29e-N29t or due to lack of data (i.e., no telehealth visits **CCI** or medical record history data available for the novel site so Table N3c, N4b, N4c, N5, N8d, N9b, N10b, N10c, N22e, N23e could not be presented).
- There was only one follow-up visit per patient so some analyses could not be presented (Table 24 and Table N24 series) or were modified (Table 25)
- Some tables duplicated content from other tables and are not presented (content for the Table 26, 27, N26 and N27 series can be found in the Table 20, 21, N20 and N21 series)
- Inferential statistical tests (e.g., ANOVA, chi-square test) were run to determine if differences between the practice clusters were statistically significant for Table 3e and Tables 8 series, Tables 10 series, Table 20 series
- A Bowker's test was used instead of a Cochran's Q test to evaluate if there were within-patient changes in OCS use (Table 31b) as the Cochran's Q test was not suitable 9 (only provides a method for testing three or more binary matched pairs).

Statistical analysis plan
D2287L00028 (EVA-26645)

AstraZeneca
27 Sep 2023

SIGNATURES

ASTRAZENECA SIGNATURES

D2287L00028 PRECISION Study 4 – Implementation

Statistical Analysis Plan for the Implementation of the US PRECISION AIRQ®,
Asthma Checklist, and Educational Resources (PRECISION Program) into
Clinical Practice Using Telehealth and In-Person Platforms: Addendum

This statistical analysis plan addendum has been subjected to an internal AstraZeneca review.

I agree to the terms of this statistical analysis plan.

AstraZeneca Study Statistician

PPD

Evidera Statistical Oversight

PPD

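### The AIRQ change analysis compares 12-month recall at baseline with 3-month recall at follow-up on items 8-10, so at stable event rates the score is expected to fall without any true change

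*SAP*

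**What the plan says.** SAP 5.1.2 covers secondary objective 2. It states: "The change in AIRQ® between initial visit and first follow-up visit will be evaluated using paired t-tests for the overall sample", and also by practice cluster (Table 15). It adds that "shift analyses will be conducted to evaluate change in AIRQ® control score between the initial and first follow-up visit" (Table 16), with counts of patients who improve, stay the same or worsen (Table 17). Tables 18-19 do the same for the final follow-up.

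The two forms differ. Items 1-7 have two-week recall on both. At the initial visit SAP 4.1.3.1 specifies "12-month recall for exacerbation-based risk questions" (items 8-10). For follow-up, SAP 4.1.3.2 cuts the "recall period to three rather than 12 months". SAP section 2 adds that at a follow-up visit "the clinical site will administer the AIRQ® three-month recall version (regardless of timing of follow-up visit").

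Scoring makes no distinction. In SAP Appendix A, "A total AIRQ® score is generated by summing the number of" Yes answers, and one set of cut points applies: 0-1 well controlled, 2-4 not well controlled, 5-10 very poorly controlled.

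Protocol 5.1.2 names the 12-month versus 3-month contrast and plans mean change by item and by total score with 95% confidence intervals. SAP 5.1.2 does not repeat the by-item part. SAP 6.1 warns that "change scores may not be representative of the entire sample", but only because more severe patients may be the ones who return. Neither SAP 6.1, Protocol 5.2.1 nor SAP Appendix B mentions the recall difference.

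**The concern.** Items 8-10 each ask whether an event happened at all within a window. Cutting the window from 12 months to 3 lowers the chance of a Yes even when the patient's event rate has not changed. The total then drifts down and patients cross cut points toward better control.

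The study has a single group, so no comparator would reveal this. The planned grouping by elapsed time does not help, because the 3-month form is used in every group. A programme with no effect could therefore be reported as producing a significant fall in AIRQ and a net shift to better control. HCP-rated control and chart exacerbations are recorded at both visits and might show a discrepancy, but the visible SAP does not link them to the AIRQ change.

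**Working it through.** **Inputs from the documents.** Recall windows of 12 and 3 months for items 8-10; two weeks for items 1-7 at both visits; 0-10 sum; cut points as above. The plan gives no event rate, SD, alpha or power for this comparison, so there is no stated figure to reproduce. Everything below assumes no true change and constant event rates.

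**Step 1. Expected fall.** For annual rate r and window t in years, P(Yes) = 1 - exp(-rt) if all patients share one rate. With gamma variation between patients (shape k) it is 1 - (1 + rt/k)^(-k). The fall is the sum over items 8-10 of P at t = 1 minus P at t = 0.25.

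Example with rates 0.5/0.5/0.05 for items 8/9/10 and k = 1:
- 12 months: 0.333 + 0.333 + 0.048 = 0.714
- 3 months: 0.111 + 0.111 + 0.012 = 0.235 (from unrounded values)
- Fall: 0.714 - 0.235 = 0.48 points, of a possible 3

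**Step 2. Control shifts and t-test.** Simulation of 400,000 patients per setting. Items 1-7 are each 35% Yes, from a one-factor probit model with within-visit correlation 0.5 and factor correlation 0.8 between visits, and have the same distribution at both visits. Items 8-10 are independent given gamma variation with k = 1. The t-test is two-sided at 0.05 (assumed), counting significant falls only, so the nominal rate is 2.5%; 4,000 subsamples were drawn per sample size.

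| Annual rates, items 8/9/10 | Expected fall, k = 0.5 to common rate | Improved / worsened | Equal windows, each way | Significant fall, n = 50 | n = 100 |
|---|---|---|---|---|---|
| 0.3/0.3/0.03 | 0.31-0.40 | 27.6% / 18.6% | 22.8% | 21% | 39% |
| 0.5/0.5/0.05 | 0.41-0.59 | 30.0% / 17.3% | 22.9% | 36% | 62% |
| 1/1/0.1 | 0.54-0.89 | 33.2% / 15.0% | 21.7% | 58% | 87% |
| 1.5/1.5/0.3 | 0.65-1.12 | 34.5% / 13.5% | 20.5% | 75% | 96% |

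Most of the improved share is ordinary reclassification that also occurs with equal windows. The artefact is the imbalance between improved and worsened. The items 1-7 sum rejects, in either direction, in 4-6% of samples.

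**Step 3. A second model.** This used different assumptions: rates 0.3/0.3/0.05, 0.7/0.7/0.1 and 1.5/1.5/0.3, gamma shape 0.8, follow-up at 1, 3 or 6 months, with overlapping windows handled. Falls were about 0.35, 0.57 and 0.77 points, nearly the same at each follow-up time. Rejection at n = 50 was about 32%, 64% and 87%. Items 1-7 alone rejected in 5.0-5.5% at n = 200.

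**Step 4. What would cancel the fall.** Exacerbation is a listed reason for visit on the Follow-up CRF (Protocol Appendix J). Suppose a share f of follow-ups are such visits, with items 8 and 9 both Yes. The fall cancels when f = fall / [(2 + P3(item 10)) - sum of P3(items 8-10)], where P3 is the 3-month probability. At 0.5/0.5/0.05 with k = 1, f = 0.480 / (2.012 - 0.235) = 27%. Over the four rate sets f is 18-56%.

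**The case against.** **Exacerbation visits could reverse the sign more easily than Step 4 suggests.** The symptom items would plausibly rise at such visits too. If items 1-7 go from 35% to 60% Yes, the denominator gains 7 × 0.25 = 1.75 and the break-even share drops to about 10/14/20/25% for the four rate sets. At 50% Yes it is 12/17/25/33%. This stands, and the net direction in the real follow-up set is uncertain. But it is a separate effect of who returns and when; an offset of unknown size does not make the two forms comparable.

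**Matched-window evidence exists elsewhere.** Protocol 3.1 and 6.1.2 compare chart exacerbations 12 months before and after the initial visit, and SAP Appendix B refers to a within-patient test of OCS use (Table 31b). That is useful context on the events behind items 8-10. It covers selected sites and consenting patients and does not correct Tables 15-17.

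**By-item change may still be intended.** The Table 15 shell is not in the documents, nothing visible withdraws the protocol's by-item analysis, and the exploratory sections are redacted. This is fair, but by-item results would not repair the total-score test or the shift tables.

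**The sizes depend on the model.** If items 8 and 9 arise from the same events, with hospital stays nested, rejection at n = 50 is 18/31/49/55% rather than 21/36/58/75%. That is smaller but still far above nominal.

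**Items 1-7 are not a clean substitute.** Regression to the mean or selective return can move them in any uncontrolled before-after comparison. True; they remove the recall artefact only.

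**Conclusion.** The concern holds. The mismatch is documented, and at stable non-zero event rates its direction follows from the arithmetic. Under the assumed rates the expected artefact is 0.31 to 1.12 points, capped at 3 and zero for patients with no events. It is enough to produce a significant fall in 21-75% of samples at n = 50 and 39-96% at n = 100 in the main model. These sizes rest on assumed rates, symptom prevalence, correlations and sample sizes, because the documents supply none of them. Confidence is high for the mismatch and its expected direction, and lower for the net bias in the actual data, where exacerbation-prompted visits could offset it. It affects a secondary objective worded as exploratory, not the primary objective. It should be fixed because Tables 15-17 cannot, as planned, separate improvement from a shorter recall window.

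**What to change.** - Make the change in the items 1-7 sum the tested result, with mean change and 95% CI.
- State in the SAP the by-item change with 95% CIs that Protocol 5.1.2 plans.
- Report items 8-10 separately, labelled with their two recall windows.
- Keep the 10-item change and the control-level shifts as descriptive, not as evidence of improvement.
- Add the recall mismatch to SAP 6.1.
- As context, show results by the Follow-up CRF reason for visit and beside the shift in HCP-rated control. That rating uses the same item at both visits, but it is not independent because the HCP sees the AIRQ.

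**Cost.** No new data. SAP Appendix B is in the past tense, so analyses appear to have been run; if so, add these as labelled supplementary analyses to Tables 15-17. Appendix B also says "There was only one follow-up visit per patient so some analyses could not be presented". First and final follow-up therefore coincide, and Tables 18-19 repeat Tables 16-17. The downside is that the items 1-7 sum is off the validated 0-10 scale, has no control cut points, omits the risk domain, and is likely to show a smaller change.

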Change in AIRQ™ score and control level between the initial telehealth visit and follow-up visit(s) (using the AIRQ™ 3-Month Recall when available) will be explored by site and cluster and presented using descriptive statistics (n, frequency, mean, and SD) and mean change of AIRQ™ by item and total score, (95% CIs computed; initial visit vs. follow-up visits) and a shift analysis for control level.

Change in AIRQ™ score and control level between the initial telehealth visit AIRQ™ (12-Month Recall) and follow-up visit(s) (using the AIRQ™ 3-Month Recall when available) will be stratified by site and cluster and presented using descriptive statistics (n, frequency, mean, and SD). Mean change of AIRQ™ by item and total score (95% CIs computed; initial visit vs. follow-up visits) and a shift analysis for control level will be conducted.

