5. ANALYSIS METHODS

5.1 Statistical Methods – General Aspects

An overall data disposition figure (Figure 1) will be generated on all enrolled patients to describe total enrolled/consented, total sample included/excluded from analyses, and finally key data (AIRQ®) availability status. In the data disposition figure, the total sample who had a follow-up visit will be reported by practice cluster. A patient disposition table will also be developed to descriptively characterize the sample in terms of total patients enrolled, age group, and language by site and practice cluster (Table 1a to Table 1c). Descriptive statistics (n, frequency, mean, median, and SD) will be used to characterize the sample in terms of the patient-reported sociodemographic and clinical characteristics (e.g., age, sex, education, etc.) (Table 2a and Table 2b, respectively), overall and by practice cluster. Descriptive statistics (n, frequency, mean, median, and SD) will be used to characterize the sample overall and by cluster type in terms of clinician-reported patient characteristics, clinical characteristics, and visit information (Tables 3a to 3f).

Descriptive statistics (n, mean [SD], median, range) will also be used to present the results (overall and by practice cluster) for the AIRQ® total and control level scores (Table 4a). AIRQ® scores will also be summarized by visit platform (telehealth vs. in-person), exacerbation history, education level, language (sample size permitting), age, sex and NAEPP step level (Table 4b to 4h). Descriptive statistics (n, mean, SD, median range) will be presented for CCI [REDACTED]

[REDACTED] Descriptive statistics (n, mean [SD], median, range) will be presented for CCI [REDACTED]

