[REDACTED] [REDACTED] [REDACTED] [REDACTED] Descriptive statistics (n, %) will be presented for the ACE Questionnaire (item scores) by practice cluster, visit platform, AIRQ® control score, exacerbation history, education level, language, age, sex, and NEPP step level (Table 7 series). Item responses and scores on the patient-reported outcome measures (AIRQ®, CCI [REDACTED] and ACE) will be compared across groups (practice cluster, visit platform, exacerbation history, education level, language, age, sex and NAEPP step level). For continuous variables, ANOVA will be used to compare mean scores across groups; pairwise comparisons between means will be performed using Scheffe's test adjusting for multiple comparisons for more than two groups. For categorical data, chi-square analyses will be used to compare frequencies by groups. No adjustments will be made for multiple groups.

For the follow-up analysis dataset, a patient disposition table will be developed to descriptively characterize the follow-up analysis set in terms of age group, language, race, and education by practice cluster (Table 8a). The mean time to first follow-up visit will be described (n, %) in Table 8b. For the primary care and specialty clusters, the first follow-up clinical CRF will be completed at the patient's first follow-up visit. For the novel cluster sites where patients are receiving multiple asthma coaching sessions, the follow-up clinical CRF will be completed at their final coaching session.

Descriptive statistics (n, %) will be used to describe patients with a follow-up visit by AIRQ® control level at initial visit (Tables 8c). Descriptive statistics (n, %) will also be used to describe patients with a follow-up visit by exacerbation history, education level, language, age, sex, and NAEPP step level at the initial visit (Tables 8d to 8i). Descriptive statistics (n, %) will be used to describe patients with a follow-up visit by HCP actions at the initial visit overall and by practice cluster (Table 8j to 8m).

Clinical characteristics and visit information from the first follow-up visit will be presented using descriptive statistics (n, mean [SD], median, range) (Tables 9a to 9e). Descriptive statistics (n, mean [SD], median, range) will also be used to present the results (overall and by practice cluster) for the first follow-up AIRQ® scores and control levels (Table 10a). AIRQ® scores from the first follow-up

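### The SAP does not carry forward the protocol's by-item AIRQ change, so its change tables cannot separate symptom improvement from the shorter recall of items 8-10

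*SAP*

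**What the plan says.** **Protocol 5.1.2** plans "mean change of AIRQ™ by item and total score, (95% CIs computed; initial visit vs. follow-up visits", together with a shift analysis for control level. The paragraph that follows repeats this almost unchanged and names the two recall versions.

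**SAP 5.1.2** covers the same secondary objective: the AIRQ change from the initial to the first follow-up visit "will be evaluated using paired t-tests for the overall sample, and by practice cluster (Table 15". If numbers allow, "change in AIRQ® score will also be evaluated based on elapsed time from initial visit to follow-up by groups". For Table 16, "shift analyses will be conducted to evaluate change in AIRQ® control score between the initial and first follow-up visit"; Table 17 counts patients whose level got better, stayed or got worse; Tables 18 and 19 repeat both for the final follow-up. A trajectory of the score over visits is also conditional on numbers.

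The single-visit summaries have the same content. SAP 5.1 plans descriptive statistics "for the AIRQ® total and control level scores (Table 4a" and "for the first follow-up AIRQ® scores and control levels (Table 10a". It mentions AIRQ item responses once, for comparison across groups such as cluster, platform and age.

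**Recall.** SAP 4.1.3.1 and 4.1.3.2 give two weeks for items 1-7 on both forms. Items 8-10 have 12 months on the initial form and three months on the follow-up form. SAP section 2 uses the three-month form whatever the interval to follow-up. SAP Appendix A defines one summed score and one set of cut-points: 0-1, 2-4 and 5-10.

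**The concern.** The protocol promised a by-item result on a named secondary objective, and the readable SAP does not deliver it. In many studies that would be a loss of detail only. Here it affects what the remaining tables can mean.

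Three of the ten items are asked over a different period at the two visits. The last three months are part of the last 12, so with accurate answers and an unchanged event rate, 'Yes' on items 8-10 can only become less likely or stay the same when the window shortens. The total, and the control level derived from it, is therefore pushed towards apparent improvement. Tables 15-19 all rest on the total or the control level. A reader of those tables could not tell whether patients had fewer symptoms or were simply asked about a shorter period.

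**Working it through.** The plan gives no figure to reproduce. The check sets the two documents side by side and then works through the scoring.

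**1. Change outputs planned**

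| Output | Protocol 5.1.2 | SAP 5.1.2 (readable text) |
|---|---|---|
| Total score | Mean change, 95% CI | Paired t-test, Table 15; no interval named |
| Each item | Mean change, 95% CI | None |
| Control level | Shift analysis | Tables 16-19 |
| Score by elapsed time; trajectory | Not planned | If numbers allow; on the score |

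None of the SAP's change outputs is by item. The item responses in SAP 5.1 are compared between groups, not between visits.

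**2. Same patient, same day, two forms** (cut-points from SAP Appendix A)

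- Patient A answers 'No' to items 1-7. One exacerbation, between three and 12 months ago, led to steroids and an unplanned visit. On the 12-month form the score is 0 + 2 = 2, not well-controlled. On the three-month form it is 0 + 0 = 0, well-controlled.
- Patient B answers 'Yes' to two of items 1-7. An episode of the same age makes items 8, 9 and 10 all 'Yes' on the 12-month form: 2 + 3 = 5, very poorly controlled. On the three-month form the score is 2 + 0 = 2, not well-controlled.

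Each moves one control level with nothing changed but the form.

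**3. What a mean change in the total can hide** (illustrative; -0.6 is not a figure from the documents)

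Mean change in the total is the sum of the changes in the proportion answering 'Yes' to each item.

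- Items 8-10 each fall by 20 points, items 1-7 unchanged: 3 × (-0.20) = -0.60.
- Items 1-7 each fall equally, items 8-10 unchanged: -0.60 / 7 = -0.086, about 9 points each.

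The mean change is the same in both cases. Only the second shows symptom change on a like-for-like recall.

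**4. Precision of a by-item paired difference**

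For a paired difference in proportions near zero, with a share d of patients giving different answers at the two visits, the 95% half-width is about 1.96 × √(d/n). The documents give neither d nor the number followed up. Assume d = 0.20:

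- n = 300: 1.96 × √(0.20/300) = 0.051, about 5 points.
- n = 100: 1.96 × √(0.20/100) = 0.088, about 9 points.
- n = 50 (one site's recruitment target, used only to show a small group): 1.96 × √(0.20/50) = 0.124, about 12 points.

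The result is usable overall at the larger sizes and imprecise in a small cluster.

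**The case against.** The strongest reply is that the SAP is silent on by-item change and does not withdraw it. The protocol is itself a plan and still specifies this output. The table shells are not in the documents, and the content of SAP 5.1.3 is redacted. A reader might infer that no planned output shows item-level change; that goes too far, and the point holds for the readable SAP only. Even so, a secondary analysis belongs in SAP 5.1.2, which is readable and names its change tables.

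Two other stronger readings are not supported:

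- *Table 15 tests an unspecified quantity.* The sentence is loose, but the objective concerns AIRQ scores, the next sentence speaks of the score, and Appendix A defines a single sum. Table 15 is evidently the total.
- *Appendix B should have disclosed the omission.* Appendix B covers revisions to analyses initially specified in the SAP. It does not log differences from the protocol, so its silence shows nothing.

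It is also fair to say that a by-item table does not rescue items 8-10. Their recall differs item by item, so a fall in 'Yes' stays confounded. Nor are single items the only way to separate the two parts: subtotals for items 1-7 and 8-10 would do it. The Follow-up CRF records exacerbations since the last visit separately, but that does not correct the AIRQ total.

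Finally, the study is descriptive and this objective is to explore. The protocol's synopsis and secondary outcome name AIRQ scores, not items, and Protocol 6.1.2 leaves discussion of individual responses to the provider's judgement. This limits the weight of the point. It does not answer the recall problem in the tables that remain.

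**Conclusion.** The point stands. Protocol 5.1.2 plans AIRQ change by item and total with 95% intervals. The readable SAP 5.1.2 keeps the total-score change, without a named interval, and the control-level shifts. Because only items 1-7 have the same recall at both visits, none of Tables 15-19 can separate symptom improvement from the effect of a shorter window.

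The direction of that effect follows from the two forms, assuming accurate answers and an unchanged event rate. Its size cannot be derived from the documents: the -0.6 change, the 20% discordance and the follow-up counts are illustrations. A reader might infer that any improvement seen would be an artefact. The documents do not support that; they show only that the planned change tables could not rule it out. The matter is worth correcting for the secondary objective and does not touch the primary one.

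**What to change.** 1. In SAP 5.1.2, state that Table 15 is the AIRQ total score and report its mean change with a 95% confidence interval.
2. Add the protocol's by-item result for the follow-up analysis set. For each of the ten items, give percent 'Yes' at the initial visit, percent 'Yes' at first follow-up, and the paired difference with a 95% interval. Show it overall, and by practice cluster where numbers allow.
3. In that table give separate subtotals: items 1-7, with the same recall at both visits and so interpretable as change; and items 8-10, labelled as not comparable across visits because the recall period differs.
4. If the by-item result is not to be produced, record and justify that as a departure from the protocol.

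The cost is one further descriptive table from responses already collected, with wide intervals in small clusters.
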